#### 5.1.1 INFORMED CONSENT

Informed consent will be obtained from all subjects prior to study participation. Informed consent is a process that is initiated prior to the individual's agreeing to participate in the study and continues throughout the individual's study participation. Extensive discussion of risks and possible benefits of participation will be provided to each participant.

Investigators have ethical and legal responsibilities to ensure that the protocol is clearly explained to each subject considered for enrollment in the study. Compliance with this requirement should be documented on a written Informed Consent Form approved by the reviewing IRB. Each Informed Consent Form will include the elements required by FDA regulations in 21 CFR Part 50.

Consent forms will be IRB-approved, and the participant will be asked to read and review the document. The investigator, or investigator-delegated study personnel, will explain the research study to the participant and answer any questions that may arise. All participants will receive a verbal explanation in terms suited to their comprehension of the purposes, procedures, and potential risks of the study and of their rights as research participants. Participants will have the opportunity to carefully review the written consent form and ask questions prior to signing. The participants should have the opportunity to discuss the study with their surrogates or think about it prior to agreeing to participate. The participant will sign the informed consent document prior to any procedures being done specifically for the study.

The IRB-approved Informed Consent Form will be signed by the study personnel obtaining consent. A copy of the informed consent document will be given to the participants for their records. The investigative site will keep the original on file. The rights and welfare of the participants will be protected by emphasizing to them that the quality of their medical care will not be adversely affected if they decline to participate in this study.

The participants may withdraw consent at any time throughout the course of the trial without any penalty or loss of benefits to which the subject is otherwise entitled. An Investigator may also discontinue a subject from the study without the subject's consent, if the Investigator feels it is in the best medical interest of the subject. The date and the reason for study withdrawal will be indicated on the Study Exit CRF.

 APYX™ MEDICAL Apyx Medical Corporation	
Protocol Number: APX-21-04	Effective Date: March 19, 2024 Revision No: 7.0
Title: Histological Evaluation of Human Skin Biopsies to Assess the Effects of Renuvion APR Treatment as an Adjunct Procedure in Facelift Surgery	

#### 5.1.1.1 CONSENT/ASSENT AND OTHER INFORMATIONAL DOCUMENTS PROVIDED TO PARTICIPANTS

Consent forms describing in detail the study device, study procedures, and risks are given to the participant and written documentation of informed consent is required prior to starting intervention/administering study product

#### 5.1.2 PRE-TREATMENT RECRUITING/SCREENING

Subjects will be recruited from the study site's patients who are scheduled or planning to schedule a lower facelift. Study site personnel will explain the design and purpose of the study to potential study subjects. Subjects interested in participating and who qualify based on the pre-screening questionnaire will proceed to the informed consent process.

#### 5.1.3.1 SCREEN FAILURES

A screen failure subject is one from whom informed consent is obtained and is documented in writing (i.e., subject signs an Informed Consent Form), but who does not receive a study treatment because of failure to meet all of the eligibility criteria. Screen failure subjects will be included in the total number of subjects enrolled (i.e., all subjects consented), but not counted towards the total subjects treated.

### 5.2 INCLUSION CRITERIA

Subjects must meet all of the following criteria for study enrollment:

- Male or female subjects, ages 18 – 75 years old.
- ASA Physical Status Classification System Class I and Class II subjects.
- Planning to undergo a lower facelift procedure, with or without a neck lift, at the investigator's site.
- Understands and accepts the obligation not to undergo any other procedures or treatments in the areas to be treated during study participation.
- Absence of physical conditions unacceptable to the investigator.
- Females of childbearing potential who are sexually active must be willing to use an approved method of birth control during study participation.
- Willing and able to comply with protocol requirements, including study-required images/photos, assessments/measurements, and returning for follow-up visits.
- Willing to release rights for the use of study photos, including in publication.
- Able to read, understand, sign, and date the informed consent.
- Able to communicate with the site via video and/or photographs, in the event of a virtual follow-up visit.

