### 4. STUDY DESIGN AND ENDPOINTS

#### 4.1 DESCRIPTION OF THE STUDY DESIGN

This study is a prospective, single-arm clinical study to be conducted at up to three clinical sites in the US. Up to 10 subjects will be enrolled and treated if they meet the inclusion/exclusion criteria and provide written informed consent.

Enrolled subjects meeting all entrance criteria and confirmed eligible for study treatment will be asked to participate. Subjects will receive a lower facelift surgery per the Investigator's standard clinical practice and treatment with the Renuvion APR System. The mid/upper-face area will not be treated with Renuvion and the lower face/neck area will be treated with Renuvion. Treatment will consist of subdermal coagulation of soft tissue using the Renuvion APR handpiece.

Standardized images will be taken prior to treatment and during each follow-up visit using the site's camera system. Baseline assessments and pre-treatment images should be obtained within 30 days of the study treatment.

 Apyx Medical Corporation	
Protocol Number: APX-21-04	Effective Date: March 19, 2024 Revision No: 7.0
Title: Histological Evaluation of Human Skin Biopsies to Assess the Effects of Renuvion APR Treatment as an Adjunct Procedure in Facelift Surgery	

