## 4.3 STUDY OUTCOME MEASURES

1. Change in histology evaluation of biopsy tissue between the untreated portion of the face and the Renuvion treated portion at the D180 visit and compared to baseline.
2. Analysis of all adverse events through the D180 follow-up visit.
3. Analysis of bruising post-procedure.
4. Analysis of swelling post-procedure.
5. Healing profile.
6. Analysis of bleeding during surgery.
7. The Principal Investigator will complete a PGAIS assessing overall aesthetic improvement in the treatment area at day 45, 90, and 180 post-treatment.
8. The subject will complete a SGAIS assessing overall aesthetic improvement in the treatment area at day 45, 90, and 180 post-treatment.
9. The subject will complete a Patient Satisfaction Questionnaire (PSQ) at the 180-day follow-up visit.
10. Change in estimated biological skin age from baseline to D180.

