#### 4.3.4.1 HISTOLOGY EVALUATION OF BIOPSY TISSUE

Tissue samples will be assessed via microscopy, histology, and immunohistochemistry for biological markers of elasticity (collagen density, elastin, fibrillin-1) and hydration (HA) at Baseline and Day 180.

[figure not shown]
The density of dermal collagen is an indicator of skin elasticity because of collagen's role in maintaining the strength of the skin, helping it to resist mechanical deformation. Other biological markers of elasticity are fibrillin-1, a glycoprotein that supports the integrity of the dermal elastic fiber network, and elastin, an essential protein of the elastic fibers of the skin, such as oxytalan and elaunin. Well-studied biological markers of skin hydration include aquaporin-3 (AQP3), water- and glycerol-transporting membrane proteins expressed in the epidermis and glycosaminoglycans (GAGs), which are linear polysaccharide molecules, including HA, that bind water and help regulate the hydration of the dermis.

Two living human skin tissue samples will be collected at baseline during the facelift procedure prior to any treatment with the Renuvion APR system and at Day 180 post-surgery (D180) during the follow up visit. Skin punch biopsies ranging from 3-5 mm in diameter will be obtained from left side of the face. One tissue sample will be taken from the untreated portion of the face within 2cm of the Root of the Helix and 2cm of the hairline. Measures should be taken to ensure the biopsy is taken from facial skin, rather than scalp skin. The second tissue sample will be obtained from cheek skin in the untreated area of the lower face within 2 cm of the treatment line. See **Figure 3**. Both biopsies will be taken prior to any treatment with the Renuvion APR System at Baseline and then again after treatment at the same locations at D180. The untreated skin tissue samples from non-surgical sites for each subject will be provided as control specimen. The tissue samples will be fixed in 10% neutral buffered formalin and prepared for histological and immunohistochemical assessments. In brief, tissues will be gross-trimmed, dehydrated, oriented

 Apyx Medical Corporation	
Protocol Number: APX-21-04	Effective Date: March 19, 2024 Revision No: 7.0
Title: Histological Evaluation of Human Skin Biopsies to Assess the Effects of Renuvion APR Treatment as an Adjunct Procedure in Facelift Surgery	

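### The bar on other procedures covers only the treated areas, so the control biopsy site may be altered before Day 180 without a deviation; cover of the cheek site is unclear

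*Combined protocol and SAP*

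**What the plan says.** **The restriction.** Among the inclusion criteria, in Section 5.2 and in the synopsis, the subject "Understands and accepts the obligation not to undergo any other procedures or treatments in the areas to be treated during study participation". The treated areas are not defined in that criterion.

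**Where the device is used.** Section 4.1: "The mid/upper-face area will not be treated with Renuvion and the lower face/neck area will be treated with Renuvion". The synopsis overview and Section 7.2 agree.

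**Where the biopsies are taken.** Under Section 4.3.4.1 one sample is "taken from the untreated portion of the face within 2cm of the Root of the Helix" and close to the hairline. The same section adds: "The untreated skin tissue samples from non-surgical sites for each subject will be provided as control specimen". The second sample is cheek skin from the lower face, no more than 2 cm from the treatment line, and the text describes that skin as untreated as well. Both locations are sampled before the device is used and again at Day 180.

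**What the samples feed.** The first outcome in Section 4.3 is "Change in histology evaluation of biopsy tissue between the untreated portion of the face and the Renuvion treated portion at the D180 visit", and also a comparison with baseline. The readouts are "biological markers of elasticity (collagen density, elastin, fibrillin-1) and hydration (HA) at Baseline and Day 180".

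**The concern.** The study has one arm, so the untreated facial site is its only concurrent comparator. The comparison is informative only if nothing other than time acts on the control skin between surgery and Day 180. The one forward-looking restriction on other procedures is tied to the treated areas, and the control site lies outside them. A subject who follows the protocol to the letter could have an aesthetic procedure at that site during follow-up.

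The protocol itself makes the mechanism plausible. Section 2.1 cites work in which a hyaluronic acid filler improved skin-quality markers, and describes radiofrequency, laser and plasma devices as acting on facial skin through collagen contraction. Collagen density and HA are among the study's own readouts. At stake is whether a treated-minus-control difference at Day 180 can be attributed to the study treatment. With at most 10 subjects, one altered control sample carries weight.

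**Working it through.** The plan has no figure to reproduce: Section 10.1 provides for descriptive statistics only, and Section 10.2 gives a ceiling of 10 treated subjects without a variance or effect size. The check is of the text, followed by a short illustration.

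**Step 1: is the control site inside the restricted area?**
- If *treated* means treated with the device, Section 4.1 excludes the mid/upper face.
- If *treated* means device plus surgery, Section 4.3.4.1 describes the control specimens as coming from non-surgical sites.
- The control site is outside on either reading. A whole-face reading is weak: where Section 5.3 means the whole region, in its exclusion for earlier procedures, it names the face and neck.

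**Step 2: does another provision close the gap?**
- Section 5.3 excludes an earlier facelift, neck lift or treatment with the device. That is history only and does not name filler, laser or other radiofrequency devices.
- Section 7.1 asks sites to document medications and prior or planned procedures. It records; it does not prohibit.
- Section 7.4.4 has one pre-biopsy exposure check at Day 180, for NSAID use.
- Section 7.4.4 also reviews protocol deviations at visits, but a permitted procedure is not a deviation as Section 14.4 defines one.
- Section 10.1 has no rule for a biopsy taken after such a procedure.

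**Step 3: is the cheek site covered?** Outcome 1 calls this tissue the treated portion, while Section 4.3.4.1 places it in lower-face skin that it calls untreated. The wording may mean only that the skin is not yet treated at the baseline sampling, or that the site lies outside the treatment line. The text does not settle which, so the reach of the restriction is uncertain here too. The two passages need to be reconciled.

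**Step 4: illustration (the numbers of affected subjects and the rates are assumptions).** Let n = 10, let k subjects have a procedure at the control site, and let each such procedure shift the control-site marker by d.

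Shift in mean control-site change = k × d / n

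| k | Shift in mean control-site change | Shift in treated-minus-control contrast |
|---|---|---|
| 1 | 1 × d / 10 = 0.1d | −0.1d |
| 2 | 2 × d / 10 = 0.2d | −0.2d |
| 3 | 3 × d / 10 = 0.3d | −0.3d |

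If the procedure improves the marker, the contrast shrinks and a device effect is masked. An unrestricted procedure at the cheek site would act with the opposite sign.

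Chance of at least one affected control biopsy, if each subject independently has probability p: 1 − (1 − p)^10.
- p = 5%: 1 − 0.95^10 = 40%
- p = 10%: 1 − 0.90^10 = 65%
- p = 20%: 1 − 0.80^10 = 89%

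**The case against.** The best case against the point is that it depends on an event for which the documents give no rate. The procedure would have to reach a small patch near the ear and hairline, not merely the upper face. That the subjects seek facial surgery does not establish how often this happens. The analysis is descriptive, and the likely error at the control site is conservative. All of this stands, and it limits the size of the point. It does not remove the gap: a descriptive contrast is moved by an altered control as much as a tested one would be.

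Four stronger readings are tempting, and the documents do not support them.

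- **That the rule protects exactly one side of the comparison.** Section 4.3.4.1 calls the cheek skin untreated as well, so cover of that side is uncertain rather than assured.
- **That nothing would reveal an affected sample.** Medications are reviewed at every visit and photographs are taken at most follow-up visits (Table 3), and subjects are interviewed about medical occurrences (Section 8.3). A site could notice a procedure. What is missing is a question that asks for it and a rule for handling the biopsy. The consent form and each site's care instructions might add a restriction, but they are not available to check.
- **That all of outcome 1 is compromised.** Outcome 1 also compares with baseline, and the treated-site change from baseline does not use the control sample.
- **That the bias can be stated in standard deviations and set against a confidence interval.** The documents give no standard deviation and plan no interval. Section 4.3.4.1 has collagen and elastin fibre integrity scored semi-quantitatively. A shift in one marker is also not on the same scale as the spread of a within-subject contrast unless a correlation is assumed.

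**Conclusion.** The gap is real and should be closed. Read as written, the restriction does not reach the control biopsy site, and its reach at the cheek site is unclear. No other provision in the documents prohibits filler, laser or radiofrequency at the control site before Day 180.

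The size is unknown. It may be zero if no subject has such a procedure. With 10 evaluable pairs, each affected control moves the mean treated-minus-control contrast by one tenth of the shift that the procedure causes, and by more if fewer pairs are available, since Section 5.5.2 does not replace withdrawals. The expected direction, if the procedure improves control-site markers, is to hide a device effect and not to create one. This rests on two assumptions: that such procedures occur in this population, and that they change the readouts at the biopsied skin. The protocol's own background makes the second plausible but gives no magnitude.

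**What to change.** 1. In Section 5.2 and the synopsis, extend the restriction by adding *or at either biopsy site* after the treated areas, and align the consent form. Naming both sites also removes the doubt about the cheek sample. Separately, reconcile the description of the cheek site in Section 4.3.4.1 with its role as treated tissue in outcome 1.
2. Add a CRF item at each visit asking about intervening facial procedures, with site and date.
3. State in Section 10.1 that outcome 1 will be reported with and without biopsies taken after such a procedure. Both results are needed, because dropping samples selects on an event after baseline.

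Cost: one phrase in two places, a consent edit, one CRF item and one sentence of analysis. A few candidates may decline to postpone upper-face procedures for 180 days, and the sensitivity analysis loses the paired contrasts of affected subjects from a total of at most 10.

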### 5.3 EXCLUSION CRITERIA

Subjects will be excluded if they meet any of the following criteria:

- Subjects presenting with ASA Physical Status Classification System Classes III or higher.
- Pregnant, lactating, or plans to become pregnant during study participation.
- Known hypersensitivity or allergy to tumescent anesthetic (lidocaine/ epinephrine).
- Known hypersensitivity or allergy to ibuprofen or other NSAIDS.
- Active systemic or local skin disease that may alter wound healing.
- Significant or uncontrolled medical condition that in the opinion of the investigator participation in the study may compromise the patient's health.
- Known susceptibility to keloid formation or hypertrophic scarring.

- Cancerous or pre-cancerous lesions in the area to be treated.
- Possesses a surgically implanted electronic device (i.e. pacemaker).
- Serious mental health illness such as dementia or schizophrenia; psychiatric hospitalization in the past two years.
- Participation in any other investigational study within 30 days prior to consent and throughout study participation.
- Subject who, in the opinion of the investigator, is not an appropriate candidate for the study.
- Subject who has had a prior facelift, neck lift, or Renuvion treatment in the face/neck area.

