Inclusion Criteria:	
 
• Male or female subjects, ages 18 – 75 years old.
 
• ASA Physical Status Classification System Class I and Class II subjects.
 
• Planning to undergo a lower facelift procedure, with or without a neck lift, at the investigator's site.
 
• Understands and accepts the obligation not to undergo any other procedures or treatments in the areas to be treated during study participation.
 
• Absence of physical conditions unacceptable to the investigator.
 
• Females of childbearing potential who are sexually active must be willing to use an approved method of birth control during study participation.
 
• Willing and able to comply with protocol requirements, including study-required images/photos, assessments/measurements, and returning for follow-up visits.
 
• Willing to release rights for the use of study photos, including in publication.
 
• Able to read, understand, sign, and date the informed consent.
 
• Able to communicate with the site via video and/or photographs, in the event of a virtual follow-up visit.
 

Exclusion Criteria:	
 
• Subject presenting with ASA Physical Status Classification System Classes III or higher.
 
• Pregnant, lactating, or plans to become pregnant during study participation.
 
• Known hypersensitivity or allergy to tumescent anesthetic (lidocaine/epinephrine).
 
• Known hypersensitivity or allergy to ibuprofen or other NSAIDs.
 
• Active systemic or local skin disease that may alter wound healing.
 
• Significant or uncontrolled medical condition that in the opinion of the investigator participation in the study may compromise the patient's health.
 
• History of autoimmune disease (excluding Hashimoto's thyroiditis).
 
• Known susceptibility to keloid formation or hypertrophic scarring.
 
• Cancerous or pre-cancerous lesions in the area to be treated.
 
• Possesses a surgically implanted electronic device (i.e. pacemaker).
 
• Serious mental health illness such as dementia or schizophrenia; psychiatric hospitalization in the past two years.
 
• Participation in any other investigational study within 30 days prior to consent and throughout study participation.
 
• Subject who, in the opinion of the investigator, is not an appropriate candidate for the study.
 

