Protocol Number: APX-21-04

Effective Date: March 19, 2024

Revision No: 7.0

Title: Histological Evaluation of Human Skin Biopsies to Assess the Effects of Renuvion APR Treatment as an Adjunct Procedure in Facelift Surgery

	
 
• Subject who has had a prior facelift, neck lift, or Renuvion treatment in the face/neck area.
 

Outcome Measures:	
 
1. Change in histology evaluation of biopsy tissue between the untreated portion of the face and the Renuvion treated portion at the D180 visit and compared to baseline.
 
2. Analysis of all adverse events through the D180 follow-up visit.
 
3. Analysis of bruising post-procedure.
 
4. Analysis of swelling post-procedure.
 
5. Healing profile.
 
6. Analysis of bleeding during surgery.
 
7. The Principal Investigator will complete a PGAIS assessing overall aesthetic improvement in the treatment area at day 45, 90, and 180 post-treatment.
 
8. The subject will complete a SGAIS assessing overall aesthetic improvement in the treatment area at day 45, 90, and 180 post-treatment.
 
9. The subject will complete a Patient Satisfaction Questionnaire (PSQ) at the 180-day follow-up visit.
 
10. Change in estimated biological age from baseline to D180.
 

Safety Variables:	
 
▪ Prior to treatment, the subject's medical history will be reviewed, a urine pregnancy test will be performed (if applicable), and a physical examination will be conducted.
 
▪ Following study treatment and at each subsequent visit, the subject will be queried about adverse events, expected treatment effects, and changes in concomitant medications, and the treatment area will be visually examined.
 

Study Duration:	The duration from when the study opens to enrollment until completion of data analyses is anticipated to be 12 months.

 Apyx Medical Corporation	
Protocol Number: APX-21-04	Effective Date: March 19, 2024 Revision No: 7.0
Title: Histological Evaluation of Human Skin Biopsies to Assess the Effects of Renuvion APR Treatment as an Adjunct Procedure in Facelift Surgery	

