## 5. SUBJECT ENROLLMENT AND WITHDRAWAL

### 5.1 STUDY POPULATION

The study population will consist of males and females between 18 and 75 years of age who have chosen to participate in this clinical trial as evidenced by execution of the informed consent document and meet eligibility criteria defined in this protocol are eligible for participation in this clinical trial. Subjects will be considered enrolled into the study when they have signed an approved informed consent form. Subjects who are enrolled and do not meet eligibility criteria will be exited as a screen fail without study treatment. A study exit Case Report Form will be completed for all enrolled subjects.

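### The synopsis excludes a history of autoimmune disease but section 5.3 does not, and the protocol does not say which list governs

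*Combined protocol and SAP*

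**What the plan says.** The exclusion criteria appear twice in the current protocol (revision 7.0).

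- **Protocol Synopsis, Exclusion Criteria.** The list has 14 items, the last carried over to the following page: "Subject who has had a prior facelift, neck lift, or Renuvion treatment in the face/neck area". One of the 14 is "History of autoimmune disease", with Hashimoto's thyroiditis exempted.
- **Section 5.3.** The list opens with "Subjects will be excluded if they meet any of the following criteria" and has 13 items. None of them mentions autoimmune disease.

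Section 5.1 ties eligibility to the protocol as a whole: those who consent and "meet eligibility criteria defined in this protocol are eligible for participation in this clinical trial". Both lists are in the protocol, and no order of precedence is given.

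Section 2.2.1.1 names restriction to eligible subjects as one of the means of limiting risk. Section 10.2 allows up to 10 treated subjects, and section 10.1 plans descriptive statistics only.

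**The concern.** An exclusion list is an operating rule. Here a subject with a past or well-controlled autoimmune condition other than Hashimoto's thyroiditis is barred on one page and not barred on another. Three things follow.

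1. Sites may select differently depending on which list they use for screening, and up to three sites are planned.
2. For such a subject, the screen-failure definition (section 5.1.3.1) and the deviation definition (section 14.4) give no clear answer. Treatment complies with section 5.3 and departs from the synopsis.
3. The protocol counts eligibility among its risk controls, so the ambiguity reaches a stated safeguard as well as the description of the population.

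The main outcome is biopsy histology of dermal collagen and elastic fibres, so it is reasonable to ask whether such subjects could differ on it. The protocol does not explain why the criterion was included and does not discuss that question.

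**Working it through.** The plan states no figure on this point, so the check is a comparison of texts with one line of arithmetic.

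**Step 1: count and pair the items.**

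| Topic | Synopsis | Section 5.3 |
|---|---|---|
| ASA class III or higher | yes | yes |
| Pregnancy or lactation | yes | yes |
| Tumescent anesthetic allergy | yes | yes |
| NSAID allergy | yes | yes |
| Active disease affecting healing | yes | yes |
| Significant or uncontrolled condition | yes | yes |
| History of autoimmune disease | **yes** | **no** |
| Keloid or hypertrophic scarring | yes | yes |
| Cancerous or pre-cancerous lesions | yes | yes |
| Implanted electronic device | yes | yes |
| Serious mental illness | yes | yes |
| Other investigational study | yes | yes |
| Investigator's opinion | yes | yes |
| Prior facelift, neck lift or Renuvion | yes | yes |
| **Total** | **14** | **13** |

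Difference: 14 − 13 = 1. Section 5.3 passes directly from the significant-or-uncontrolled item to "Known susceptibility to keloid formation or hypertrophic scarring"; the synopsis has the autoimmune item between those two. There is no redaction mark at that place.

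**Step 2: look for a recorded reason.** Appendix B has no entry, in any version, on adding or removing an autoimmune criterion. The version 7.0 entry records a new prior-procedure exclusion in section 5.3, and that item now stands in both lists. This suggests that the lists are meant to mirror each other.

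**Step 3: see whether another criterion does the same work.**

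- "Active systemic or local skin disease that may alter wound healing" requires disease that is active and may affect healing. A history is not enough.
- The next item requires a condition that is significant or uncontrolled and that, in the investigator's opinion, may compromise health. A mild, controlled condition need not meet it.
- Section 5.2 admits ASA class II, which section 4.3.4.7 describes as mild systemic disease. The ASA limit does not remove mild, controlled cases.
- "Subject who, in the opinion of the investigator, is not an appropriate candidate for the study" and the section 5.2 item on physical conditions unacceptable to the investigator permit exclusion case by case but do not require it. Both also stand in the synopsis, where the autoimmune item is listed separately.

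No other criterion bars a history of autoimmune disease as such.

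**Step 4: size.** With n treated subjects, one affected subject is 1/n of the sample. Since n is at most 10, 1/n is at least 1/10 = 10%.

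**The case against.** The strongest reply is that the practical gap is narrow. The investigator has several discretionary grounds for declining a subject, and these may catch some or all of the cases in question. The lists can also be satisfied together: section 5.1 refers to the protocol's criteria without limiting them to section 5.3, so a site that applies both lists would exclude these subjects. Both points stand. They reduce the number of subjects likely to be affected, but they do not settle which list a site must use, and discretion is not a rule.

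Some stronger readings are tempting and are not supported.

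- *Sites will enrol barred subjects.* Section 5.1 defines enrolment as signing consent, which comes before eligibility is confirmed. The issue is who can be treated, and section 5.3 permits such treatment without making it certain.
- *Eligibility deviations in general cannot be judged.* The conflict concerns one criterion; the other 13 agree.
- *The histology results would be biased by a known amount.* The protocol says nothing about autoimmune disease and collagen or elastin. Assuming that one subject's change lies 1 to 3 SD from the rest would move a mean of 10 by 0.1 to 0.3 SD, but the protocol supplies neither that assumption nor an SD. The fibre scoring is semi-quantitative (section 4.3.4.1), so a mean in SD units may not suit it. Outcome 1 also compares each subject's treated site with their own untreated site and with baseline, so a stable systemic influence on both would partly cancel.

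**Conclusion.** The point holds as an internal contradiction in one exclusion criterion. The synopsis has it, section 5.3 omits it, the other 13 agree, and neither a precedence rule nor the revision log resolves the difference. A subject with controlled or inactive autoimmune disease can be treated under section 5.3 although the synopsis bars them, and the deviation status of that subject is undefined.

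The only size the documents support is the weight of an affected subject: at least 10% of a treated sample of up to 10. How many such subjects there are, if any, is unknown. Any effect on histology or healing remains a plausible inference without a figure. The conclusion rests on the current text of both lists and on no assumption about biology. It does not say which list is right. The correction is worth making because it is cheap and the criterion belongs to a stated risk control.

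**What to change.** 1. Reconcile the synopsis and section 5.3 by amendment under section 15.2 so that the two exclusion lists are identical. The sponsor decides whether the criterion stands in both or in neither, and records the decision and its reason in Appendix B.
2. Check the recorded medical histories of subjects already treated against the synopsis criterion. Sections 7.1 and 7.4.2 already require a history. It is a brief one taken to each investigator's usual standard, so a site may need to confirm an unclear entry.
3. Identify any treated subject who meets the criterion in the subject-level histology and adverse event listings. In a descriptive study of this size, that lets a reader see whether the findings depend on them without a separate analysis.

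The cost is a small amendment with IRB review and a records check on at most 10 treated subjects. If the criterion is kept and recruitment is still open, which the documents do not show, the eligible pool may be slightly smaller.
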